#### 11.8.1.1 Sensitivity analysis of the primary endpoint

In addition to the primary analysis, several sensitivity analyses will also be employed as below:

- Pain intensity on movement measured at scheduled time points from 0-48 hours following test drug administration, adjusted for rescue medication use. The adjustment algorithm will be as such: If the scheduled pain on movement score has been assessed within one plasma half-life after the use of rescue medication (IV or oral opioid, or acetaminophen), the worst pain score from all observed ones prior to using rescue medication, if this score is higher than the pre-rescue pain score, will be used to substitute the scheduled pain score.
- Pain intensity on movement measured at scheduled time points from 0-48 hours following test drug administration will be analyzed by a mixed effect ANOVA model of repeated measures (MMRM) (i.e. no adjustments for rescue medication use)
- Analyze the observed cases without imputation for missing pain scores
- Analyze completers over 0-48 hours following test drug administration only
- Treat all missing pain as “failures” using WOCF imputation.

#### 11.8.2 Secondary Efficacy Endpoints

For all secondary efficacy endpoints, data from SABER®-Bupivacaine arm in Part 1 will be combined with the same treatment arm in Part 2. The integrated data will be compared to Bupivacaine HCl.

The key secondary efficacy endpoint:

- Pain intensity on movement measured at scheduled time points from 0-72 hours following test drug administration, adjusted for prior rescue medication use and analyzed by a mixed effect ANOVA model of repeated measures (MMRM).

The adjustment algorithm for rescue medication use is the same as described for the primary endpoint in [Section 11.8.1](#).

Additional secondary efficacy endpoints:

- Total IV morphine-equivalent dose of rescue opioids used during 0-72 hours following test drug administration (standard conversion factors will be used to convert different opioids to IV morphine-equivalents; CCI)

- Composite endpoint of Silverman's Integrated Analgesic (SIA) assessment score (Dai et al, 2013 and Silverman et al, 1993) over 0-72 hours following test drug administration
- Proportion of patients taking no opioid rescue medication from PACU discharge until 72 hours after test drug administration
- Time to first opioid rescue medication use after discharge from the PACU
- Time to PACU discharge eligibility as assessed by mPADSS (Chung, 1995; Awad and Chung, 2006).

The total IV morphine-equivalent dose of opioid rescue medication used during the first 72 hours post-dose will be analyzed by an ANOVA model adjusted for the stratification or by the van Elteren test (a stratified Wilcoxon Rank Sum test), depending on whether normality assumptions have been met.

A composite endpoint, Score of Integrated Analgesia (SIA) (Dai et al, 2013 and Silverman et al, 1993), that integrates pain assessment score with opioid use will be derived at 24, 48 and 72 hours post-surgery. The score derived for each subject represents a sum of the ranks (ranging from -200 to 200 with -200 being the best case and 200 the worst case). SIA will be analyzed by repeated measures ANOVA. The model will have treatment, sex, sex\*treatment interaction and study site as the main effects, subject as the random effect and time as the repeating factor.

[figure not shown]
The categorical efficacy endpoint, proportion of patients taking no opioid rescue medication will be compared between the two treatment groups using the Cochran-Mantel-Haenszel (CMH) test stratified by sex.

Time to the first use of rescue opioid after discharge from PACU will be analyzed using the Kaplan-Meier method. Subjects who do not use any rescue opioids will be censored at 72 hours. The stratified Log rank test will be used to compare the treatment groups.

Time to PACU discharge eligibility by mPADSS will be analyzed by Kaplan-Meier method and compared between the treatment groups by stratified Log rank test.

CCI

CCI

CCI

#### 11.8.4 Adjustment for Multiple Hypotheses Testing

The serial gate-keeping approach (proposed by [Westfall and Krishen, 2001](#)) will be used to test the primary and secondary endpoints (order by its clinical relevance and importance) in the above specified sequence. It will be implemented in the following way: If (and only if) the null hypothesis associated with primary endpoint has been rejected at the 0.05 level, then the first secondary endpoint, movement pain adjusted for rescue medication use during the first 72 hours following administration of test drug will then be tested. If this second gate-keeping step has been passed, the next secondary endpoint will be tested until the p-value > 0.05, then no more formal hypothesis testing will be performed. Once this occurs, the additional endpoints will be analyzed in order to engender additional hypotheses concerning their effects.

#### 11.8.5 Subgroup Analysis

Subgroup analyses will be conducted by age (< 45, 45-to-65, > 65), sex, and race for the primary and secondary efficacy endpoints. ANOVA analyses described for the analysis of the primary and secondary efficacy endpoints will be repeated at the subgroup level for the above-mentioned subgroups. In the subgroup analysis by sex, the sex stratum and the interaction of sex by treatment effects will not be included in the model.

Similar subgroup summaries will be also be provided for adverse events, where appropriate.

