### 5.3 Population

The trial population will consist of adult patients (males and females, 18 years of age and older) undergoing elective outpatient laparoscopic cholecystectomy under general anesthesia. In Part 1, approximately 90 patients will be randomized. In Part 2, approximately 274 eligible patients will be randomized in order to obtain 264 evaluable patients (i.e., patients who received test drug). It has been estimated that 4% of randomized patients may not receive any test drug due to unforeseeable intra-operative exclusion criteria such as need to convert to open laparotomy or need for a fifth port and trocar.

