**6.0 Trial Conduct****6.1 Investigative Sites**

The trial will be conducted at a minimum of 5 and up to 25 investigative sites in the United States.

Investigative sites will be selected based on experience in conducting analgesic studies and access to the selected patient population through either general surgery practices or hospitals where a general surgeon qualified by training or experience is available to perform or oversee procedures required by the protocol.

Each Investigator participating in this trial will meet the following criteria:

- Appropriate qualifications including current medical license, applicable certificates or personnel/sub-investigators with certificates (e.g. Drug Enforcement Administration [DEA] documentation regarding prescribing of Schedule II and higher drugs), and adequate GCP knowledge
- Availability of accessible, interested, and well organized support staff
- Availability of diagnostic facilities to support trial data requirements
- Adequate test drug storage facilities
- Availability of physician emergency response at all times

A full description of the Investigator responsibilities has been included in [Appendix 6](#).

If a given investigative site approaches randomization of 20% of the total number of evaluable subjects (264) into Part 2 of the trial, the Sponsor will assess the appropriateness of allowing the center to continue randomizing additional subjects into the trial based upon factors such as monitored site performance including documentation and protocol compliance.

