#### 11.0 Statistical Methods and Data Analysis

##### 11.1 Trial Design Considerations

###### Part 1

This part will be a randomized, parallel-group, double-blind, placebo-controlled, multi-center trial evaluating the safety and efficacy of SABER®-Bupivacaine 5 mL in patients undergoing elective outpatient laparoscopic cholecystectomy.

CCI

CCI [REDACTED]

Part 2

This part will be a randomized, parallel-group, double-blind, active-controlled, multi-center trial evaluating the safety and efficacy of SABER®-Bupivacaine 5 mL in patients undergoing elective outpatient laparoscopic cholecystectomy.

The primary efficacy objective will be to investigate whether SABER®-Bupivacaine will significantly reduce pain compared to bupivacaine HCl (75 mg) over 48 hours following test drug administration in patients undergoing laparoscopic cholecystectomy.

It has been planned that the data from centers that participate in this trial will be combined such that an adequate number of subjects will be available for analysis.

Unless otherwise specified, all statistical tests will be conducted employing a two-sided significance level of 0.05.

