**11.2 Sample Size Determination**

Part 1

One hundred fifty three subjects enrolled in each treatment group of the study will result in 90% power (assuming type 1 error rate of 5%) to detect a difference between 5 mL of SABER®-Bupivacaine and 5 mL of saline placebo CCI [REDACTED]

[REDACTED] The size of the final enrollment will be approximately 90 subjects determined by the readiness of sites to enroll subjects under IRB-approved Part 2.

Part 2

One hundred thirty-two subjects enrolled in each treatment group of the study will result in 90% power (assuming type 1 error rate of 5%) to detect a difference between 5 mL of SABER®-Bupivacaine and 15 mL of 0.5% bupivacaine HCl CCI [REDACTED]

CCI

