##### *Alternate hypothesis:*

There is a difference in analgesic effect between subjects treated with SABER®-Bupivacaine and those treated with bupivacaine HCl, as measured by pain intensity on movement scores over 0-48 hours following test drug administration, with adjustment for sex effect and imputation for missing pain scores.

The pain scores will be analyzed by a mixed effect ANOVA model of repeated measures (MMRM). The model includes the following fixed effects: sex stratum, treatment, sex by

treatment, time, interaction of treatment and time, study site and interaction of study site and treatment, with time as the repeating factor and subject as a random effect.

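### Repeating the primary MMRM with its site-by-treatment term inside age and race subgroups will usually leave small subgroups without an estimable treatment effect when there are ten or more sites

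*Combined protocol and SAP*

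**What the plan says.** Section 11.8.5 plans subgroup analyses by three age bands (under 45, 45 to 65, over 65), sex and race for the primary and secondary efficacy endpoints. The ANOVA analyses already described "will be repeated at the subgroup level for the above-mentioned subgroups". One simplification is given: in the sex subgroups, "the sex stratum and the interaction of sex by treatment effects will not be included in the model". Nothing is removed for age or race.

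The model being repeated is in 11.8.1. Its fixed effects are sex, treatment, sex by treatment, time, treatment by time, and "study site and interaction of study site and treatment, with time as the repeating factor and subject as a random effect". The 0-72 h key secondary endpoint in 11.8.2 is also an MMRM. Its fixed effects are not restated, so the same model is implied.

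Two other provisions bear on the point. Section 11.8.6 pools sites that enrol three or fewer patients. Section 11.3 randomizes in blocks of four stratified by sex and does not name site as a stratum. No fallback is given for a contrast that cannot be estimated.

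**The concern.** With a fixed site-by-treatment term, the overall treatment difference is an average of the site-specific differences. A site that contributes patients from one arm only has no such difference, so the average is undefined over the sites represented. In all of Part 2 that is uncommon when sites are few and of reasonable size. In a subgroup of a few dozen patients spread over many sites it becomes the normal case.

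The pooling rule does not prevent this if read literally. A site with 12 patients, one of them over 65, is not pooled, yet in the over-65 analysis it is a one-armed site.

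At stake is whether the planned subgroup results for the main pain endpoints can be produced by the stated method. If they cannot, the report shows blanks for the smallest groups or relies on a reduced model that the plan does not specify.

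**Working it through.** **Inputs from the documents.** Part 2: "approximately 274 eligible patients will be randomized in order to obtain 264 evaluable patients" (5.3). Sites: "a minimum of 5 and up to 25 investigative sites in the United States" (6.1). Allocation is 1:1 in blocks of four within sex (11.3). Sites of three or fewer are pooled by total enrolment (11.8.6). Model terms are those of 11.8.1.

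**Assumptions, because the documents give no figure.** Subgroup share 5, 10, 15 or 20% of 264, which is about 13, 26, 40 or 53 patients; 70% women; sites of equal or uneven size; each site weighted equally in the contrast.

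**The plan's own figure.** With 4% not dosed, 264 / 0.96 = 275, against 274 stated. This is within rounding, so 264 is a fair base. The plan gives no figure for subgroup estimability.

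**Criterion.** With K sites represented in the subgroup, the contrast is (1/K) × the sum over sites of (mean on SABER-Bupivacaine − mean on bupivacaine HCl), adjusted for sex. A contrast L is estimable only if adding L as a row to the design matrix X leaves its rank unchanged.

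**Hand check.** If a site has m subgroup patients and arms are close to independent within site, the chance that all are in one arm is 2 × (1/2)^m: 1 for m = 1, 0.5 for m = 2, 0.125 for m = 4. Forty patients spread exactly evenly over 10 sites gives four per site, and the chance of no one-armed site is (1 − 0.125)^10 = 0.26. Uneven counts lower this. Forty patients over 25 sites is 1.6 per site, so if all 25 are represented some must have a single patient and the contrast cannot be estimated.

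**Simulation.** 300 trials per setting, with the rank test on sex, treatment, sex by treatment, site and site by treatment. Proportion estimable under the plan's model (equal / uneven site sizes):

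| Sites | n≈13 | n≈26 | n≈40 | n≈53 |
|---|---|---|---|---|
| 5 | 0.04 / 0.03 | 0.42 / 0.27 | 0.81 / 0.50 | 0.97 / 0.61 |
| 10 | 0.00 / 0.00 | 0.01 / 0.01 | 0.07 / 0.04 | 0.21 / 0.08 |
| 15 | 0.00 / 0.00 | 0.00 / 0.00 | 0.00 / 0.00 | 0.01 / 0.01 |
| 25 | 0.00 / 0.00 | 0.00 / 0.00 | 0.00 / 0.00 | 0.00 / 0.00 |

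The Monte Carlo standard error is at most √(0.25/300) = 0.03. A repeat gave 0 to 23% for 10 to 25 sites and about 4 to 94% for 5 sites, which is the same picture. With 25 sites and 40 patients, about 60% of the sites represented have one arm only. Larger groups are not safe either: at about 106 patients (40%) the figures are 0.06 to 0.43 with 15 sites and 0.00 with 25.

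**Reduced models, over all site counts.**

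| Terms removed | n≈13 | n≈26 to 53 |
|---|---|---|
| site by treatment | 0.18 to 0.69 | 0.83 to 1.00 |
| site by treatment and sex by treatment | 0.65 to 0.98 | 0.98 to 1.00 |

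The repeat put the lower end for n≈13 at 0.64. Neither row includes any pooling at subgroup level.

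**Limit of the check.** It uses Part 2 patients only. The 0-72 h analysis adds Part 1 patients on SABER-Bupivacaine (11.8.2). They cannot fill an empty bupivacaine HCl cell, and this addition was not simulated.

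**The case against.** A reader might infer that the subgroup effect cannot be estimated at all. The documents do not support that. They allow as few as 5 sites and give no age or race distribution. With 5 equal-sized sites and a 15 to 20% subgroup, the contrast was estimable in about 80 to 97% of trials. Differences at individual sites with both arms also remain estimable.

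A reader might also infer that every secondary endpoint is affected. In 11.8.2 the SIA model lists site but no site-by-treatment term, and the opioid-dose ANOVA is adjusted for the stratification only. The no-opioid proportion and the time-to-event endpoints are not analysed by ANOVA. The problem is confined to the MMRM endpoints.

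The pooling rule could be re-applied to the subgroup data, since 11.8.5 repeats the analyses to which the rule belongs. The word used in 11.8.6 is about enrolment, which favours the total count, but the other reading is possible. It helps without curing the problem: the contrast was then estimable in about 55 to 95% of trials.

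It is tempting to say that a reduced model would be chosen after unblinding. Section 11.11 requires deviations to be documented before unblinding, so that outcome is a risk, not something the plan provides for.

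Finally, the subgroups lie outside the gate-keeping sequence of 11.8.4, and a non-estimable contrast fails visibly without biasing anything. That is correct and limits the weight of the point. The same term is in the primary model itself (estimable in 0.64 to 0.84 of trials for all of Part 2 with 25 sites), but that is a separate question about 11.8.1.

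**Conclusion.** The point stands for the 0-48 h MMRM and, by implication, the 0-72 h MMRM. Taken as written, 11.8.5 sets a model for the age and race subgroups that will usually give no overall treatment estimate in small groups with 10 or more sites (about 0 to 23% estimable). With 5 sites the outcome ranges from about 4 to 94%.

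These figures rest on the assumed subgroup shares of 5 to 20%, 70% women, the simulated site-size patterns and equal weighting of sites. The direction does not depend on fine detail: the result for 15 or 25 sites is close to zero throughout.

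The subgroup rule does not affect the primary test, its error rate or the sample size. It should be corrected because it is a stated rule for the main endpoints that often cannot be carried out.

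**What to change.** Add to 11.8.5, before unblinding, wording such as: *Subgroup MMRMs omit the site-by-treatment interaction for every subgroup factor and, in the age and race subgroups, also omit the sex-by-treatment interaction. Site is kept as an additive effect. Within each subgroup, sites with three or fewer patients, counted over both arms together, are pooled.*

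Pooling should go by the both-arm count. Pooling by whether a site has both arms needs the treatment codes and is unnecessary once site is additive. Sex-by-treatment has to go as well, because removing site-by-treatment alone still leaves groups of about 13 estimable in only 18 to 69% of trials.

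With both interactions removed, estimability is about 98 to 100% for about 26 patients or more and about 64 to 98% for about 13, before any subgroup-level pooling. The cost is a few lines of text and no new data. The small downside is that variation of the effect by site and by sex is not modelled within subgroups.

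### Section 11.8.5 studies age and race only by refitting the analysis within each level, so the plan as visible has no test of whether the treatment effect differs by age or race

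*Combined protocol and SAP*

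**What the plan says.** Section 11.8.5 sets the scope: "Subgroup analyses will be conducted by age (< 45, 45-to-65, > 65), sex, and race for the primary and secondary efficacy endpoints". Its method is that the ANOVA analyses "will be repeated at the subgroup level for the above-mentioned subgroups". For the by-sex analysis it adds that "the sex stratum and the interaction of sex by treatment effects will not be included in the model". It names no interaction test for age or race and gives no rule for interpreting the subgroup results.

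The primary MMRM is specified in Section 11.8.1, under the alternate hypothesis, in a sentence that runs over a page break: "The model includes the following fixed effects: sex stratum, treatment, sex by" and then "treatment, time, interaction of treatment and time, study site and interaction of study site and treatment". Sex by treatment is therefore in the full-data primary model, while age and race are not in it in any form.

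In Section 11.8.2 the SIA model also has a sex-by-treatment term; the list of effects ends "interaction and study site as the main effects, subject as the random effect and time as the repeating factor". The proportion taking no rescue opioid is compared "using the Cochran-Mantel-Haenszel (CMH) test stratified by sex", with no homogeneity test stated. The key secondary endpoint is also an MMRM, but its terms are not listed separately.

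Section 11.1 says that, unless otherwise specified, "all statistical tests will be conducted employing a two-sided significance level of 0.05". The gatekeeping sequence in Section 11.8.4 covers the primary and secondary endpoints and does not mention subgroups.

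**The concern.** The purpose of a subgroup analysis is to ask whether the treatment effect varies across levels of a factor. A separate model in each level answers another question: whether an effect can be shown in that level taken alone. The answer depends heavily on how many patients the level contains. A treatment-by-subgroup term in one model compares the levels directly.

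For age and race the plan supplies only the separate models. A reader of the trial report would have a set of within-level results and no formal comparison between them. A small band, such as patients over 65, could easily miss p<0.05 while a larger band reached it, and this could be mistaken for a real difference in benefit. The primary conclusion is not at stake. What is at stake is whether statements about older patients or particular racial groups can be supported.

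**Working it through.** **Side-by-side reading**

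| Factor | Separate models (11.8.5) | Interaction term in a full-data model |
|---|---|---|
| Age | yes | none visible |
| Race | yes | none visible |
| Sex | yes | primary MMRM (11.8.1) and SIA (11.8.2) |

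**Inputs for the illustration.** From Section 11.2: 132 per arm in Part 2, 90% power, 5% type 1 error. From Section 11.1: two-sided testing. The effect size is redacted, so the plan's figure cannot be reproduced independently, only inverted:

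- δ/SD = (1.960 + 1.282) × √(2/132) = 3.242 × 0.1231 = 0.399.
- Forward check at 0.40: n = 2 × 3.242² / 0.40² = 131.4, which rounds up to 132 per arm.

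**Assumptions.** The same effect (0.399 SD) in every age band; a simple two-sample t-test in place of the MMRM; independent bands; equal arms within bands. The documents do not give the age shares, so three splits are shown.

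**Formula.** With n per arm in a band, power comes from the noncentral t distribution with 2n − 2 degrees of freedom and noncentrality 0.399 × √(n/2). Then P(mixed) = 1 − P(all significant) − P(none significant).

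| Age shares | n per arm | Power by band | All significant | None significant | Mixed |
|---|---|---|---|---|---|
| Equal thirds | 44 / 44 / 44 | 0.4565 each | 0.095 | 0.161 | 0.744 |
| 50/35/15 | 66 / 46.2 / 19.8 | 0.624, 0.475, 0.231 | 0.069 | 0.152 | 0.780 |
| 60/30/10 | 79.2 / 39.6 / 13.2 | 0.704, 0.418, 0.166 | 0.049 | 0.144 | 0.807 |

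Worked for 50/35/15:

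- All significant: 0.624 × 0.475 × 0.231 = 0.069.
- None significant: 0.376 × 0.525 × 0.769 = 0.152.
- Mixed: 1 − 0.069 − 0.152 = 0.78.

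**No effect anywhere.** P(mixed) for three bands = 1 − 0.95³ − 0.05³ = 0.1425, about 14%.

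**Comparison.** An interaction test at 0.05 signals a difference in 5% of trials when the effect is the same in all bands, whatever the size of that effect.

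**Limits of the interaction test.** Suppose there are two equal groups (66 per arm each) and the effects differ by the whole 0.399 SD. The standard error of the difference in effects is √(2/66 + 2/66) = 0.246 SD and the ratio is 0.399/0.246 = 1.62. Power is Φ(1.62 − 1.96) = 0.37. With a 70/30 split it is 0.32.

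**The case against.** **Sex.** A reader might infer that the plan lacks an interaction test for all three factors and that it removes one for sex. The documents do not support this. Sex by treatment is in the full-data primary and SIA models. Dropping it from a model fitted to one sex is unavoidable, because sex does not vary there.

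**Interpretation rule.** A reader might also infer that the sponsor will declare differential effects by comparing p-values. Section 11.8.5 does not say so. Subgroups have no place in the formal testing sequence, and Section 11.5 provides 95% confidence intervals where appropriate. Showing estimates by level is ordinary practice. This objection stands in part. The mixed-significance figures describe how within-level tests would behave, and they do harm only if someone reads them as evidence of heterogeneity. But the plan offers no other comparison for age or race, and repeating the analyses repeats their tests at the default 0.05 level.

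**Size.** One could quote the chance that at least one band is non-significant, which is 93% at 50/35/15 (1 − 0.069). That overstates the problem, because it includes the 15% of trials in which no band is significant and there is no contrast to misread. The relevant figure for that split is 78%.

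**Visible text.** Part of Section 11.8 is redacted, and Section 11.6 refers to a separate SAP that is not in the supplied text. An interaction test for age or race could be specified there. The point is therefore limited to what can be read.

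**Conclusion.** The point holds for age and race. The visible plan relies on separate models and contains no term that could test whether the effect differs by either factor. For sex, what remains is narrower: the term exists for the primary endpoint and SIA, but the plan does not say that it will be reported as the test of heterogeneity.

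With an identical effect in all patients, mixed significance across three age bands would occur in about 74% of trials with equal thirds, 78% at 50/35/15 and 81% at 60/30/10, against a 5% false-signal rate for an interaction test. These figures rest on an effect of about 0.40 SD inferred from the sample size, a two-sample t-test in place of the MMRM, and assumed age shares. They apply to the Part 2 primary comparison. Nothing was calculated for race, because the documents give no expected composition.

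This is a worthwhile improvement to an exploratory analysis. It is not a threat to the primary result.

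**What to change.** For age and for race, replace the separate refits with one full-data model per factor containing subgroup and treatment-by-subgroup terms. Keep the analysis set that the plan already specifies for each endpoint: Part 2 mITT for the primary, and for secondary endpoints the integrated set in which the Part 1 SABER-Bupivacaine arm joins the same arm in Part 2 (Sections 11.5 and 11.8.2).

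From each model, report the treatment effect in each level with its 95% confidence interval and one interaction p-value per factor, labelled exploratory. For sex, report the existing sex-by-treatment term as the heterogeneity test.

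The cost is SAP wording and a small programming change before unblinding, with no new data. The drawback is low power, about 0.37 in the favourable two-group case worked above. The text should therefore say that a non-significant interaction does not show that effects are equal, and that the estimates and intervals carry most of the information.
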